### 6.4.2 Efficacy criteria for study stopping

We do not expect to see a greater efficacy of low-dose tamoxifen compared to the standard tamoxifen regimen for breast cancer risk reduction in any risk population. The NSABP P-1 trial found an overall magnitude of risk reduction of 49% with the standard tamoxifen regimen of 20mg per day for 5 years (risk ratio 0.51, 95% CI 0.39–0.66), with higher efficacy observed among women with

higher baseline risk. Specifically, the subgroup of women with a prior history of atypical hyperplasia had a reduction in breast cancer risk of 86% (risk ratio 0.14, 95% CI 0.03–0.47) [33]. We believe that a similar risk reduction among radiation exposed CAYAC survivors would be of sufficient clinical significance to warrant early trial stopping and reporting of results. Thus, if a risk ratio of 0.14 or less is observed during DSMB review, the trial will be halted and subjects unblinded.

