*Magnitude of risk of BC after radiation exposure:* Reported standardized incidence ratios (SIR) or relative risks (RR) for BC in this population range from 11.6 to 136.0, with the highest risk estimates generally from relatively smaller single institution studies [7-9]. From the single institution study with the largest number of women exposed to chest RT prior to 21 years of age (N=307), Wolden *et al* reported a RR of 26.2 [10]. A population-based study by Metayer *et al* reported a RR of 11.6 derived from 2,737 women who were diagnosed with HL prior to 21 years of age identified from nine U.S. NCI SEER registries and selected European countries [11]. Within this cohort, 62 girls and young women diagnosed between ages 10 and 21 subsequently developed BC. Another population-based study, the British Childhood Cancer Survivor Study (British CCSS), which included 16 cases of BC among 383 women who were treated for HL prior to 15 years of age [12], reported a similar SIR of 13.3. In contrast, in an international population-based study, Maule *et al* reported a SIR of 20.9 and an absolute excess risk of 40.6 based on 6 cases of BC that developed in 422 women with a prior diagnosis of HL occurring before age 15 [13]. Bhatia *et al* from the multi-institutional Late Effects Study Group (LESG) reported an excess risk of 55.5 based on 29 cases of BC among 480 women diagnosed with HL prior to age 17 [14]. On the other hand, Kenney and colleagues reported an SIR of 24.7 in women who were treated for a pediatric cancer with chest RT prior to age 21 from the 26-institution U.S. Childhood Cancer Survivor Study (CCSS) [15]. With 95 cases of BC among 6,068 female pediatric cancer survivors, this study had a significantly larger number of women with BC, and thus may provide a more robust estimate. In addition, the risk estimate from the CCSS study included all pediatric cancers prior to BC, with a consequent heterogeneity of radiotherapy doses and fields, while the other risk estimates were based only on HL survivors. Thus, it is clear that the risk of BC is elevated in all radiation-exposed pediatric cancer survivors.

*Long latency between radiation exposure and diagnosis of BC:* The risk of BC does not begin to increase until approximately 8 years after chest RT, and the median age at BC diagnosis is 32 to 35 years, based on the LESG and CCSS studies [14, 15]. The British CCSS reported that by twenty-five years of follow-up, the cumulative risk of BC was 12.2%.

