*Risk of BC with attained age:* Both the LESG and CCSS studies reported cumulative incidence of BC to be 13.9% and 12.9% by age 40 and 20% and 22% by age 45, respectively. Cumulative incidence rates reported by Travis *et al* ranged from 4.1% to 39.6% by age 30, depending on the age at diagnosis and amount of radiation received

[16]. For perspective, among *BRCA1* or *BRCA2* gene mutation carriers, the estimated cumulative incidence of BC at age 30 ranges from 1-5% and at age 40 ranges from 10-19% [17-20]. Thus, the risk for developing BC among HL survivors appears to exceed that of *BRCA* mutation carriers, especially before age 30 (4-40% in HL survivors compared to 1-5% in *BRCA* carriers). For survivors of other cancers, the risk appears to be elevated approximately 2-fold, similar to the degree of elevated risk for which standard-dose tamoxifen is typically offered. Importantly, in none of the studies of women treated with chest RT was a plateau of BC risk with increasing interval of follow-up observed (Figure 7, page 14).

*Risk modification by radiation dose, age, endogenous hormones, and family history:* Bhatia *et al* demonstrated preliminary evidence for an increasing risk of BC with a radiation dose of 26 Gy or more [14]. This has been confirmed by the CCSS, where a clear dose-response relationship is evident between the dose of RT to the chest and the risk of subsequent BC down to exposures of 15 Gy (Figure 2) [15]. Using a case-control design, Travis *et al* confirmed that BC risk was related to the dose of RT [21]. Following 23.1-37.1 Gy and 37.2-61.3 Gy radiation delivered to the site where a secondary BC later appeared, the RR was 8.5 and 10.5, respectively. In Figure 3, Travis *et al* clearly demonstrates that BC risk increases with dose of radiation and latency from exposure to radiation. A novel finding in this study was a protective effect of exposure to an alkylating agent (AA) or radiation to the ovaries with respect to the development of BC following chest RT (Figure 3). While still having an increased BC risk compared to population rates, those who received chest RT plus an AA or pelvic RT had a significantly lower BC

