## 4.0 **RECRUITMENT STRATEGY**

Via the Consortium for Pediatric Interventional Research (CPIR), a consortium of five institutions, including the *City of Hope National Medical Center (COH)*, *St. Jude Children's Research Hospital (SJCRH)*, *Emory University (EU)*, *University of Michigan (UM)*, and *Princess Margaret Hospital in Toronto (PMH)*, we have constructed a cohort of HL survivors who were exposed to chest RT during childhood or young adulthood, at least 5 years prior to study participation. This cohort will form the initial basis from which accrual in this trial will be conducted. Other sites and additional CAYAC diagnoses treated with RT involving the chest may be added as needed to complete accrual for the trial.

Recruitment will be conducted both prospectively and retrospectively as described below. Because this is a highly motivated patient population, at study activation we anticipated that it would be feasible to achieve a recruitment yield of 30%, and that the accrual goal of 230 would be achievable across the CPIR participating institutions described above. After the initial two years of accrual, we observed an average recruitment yield of only 14%. Therefore, new sites were recruited, and additional sites have been identified and will be recruited as needed to reach the accrual goal.

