### 8.2.3 Data and Safety Monitoring Plan

Participants enrolled on this study will be monitored by the UAB Comprehensive Cancer Center’s Clinical Trials Monitoring Committee (CTMC). Adverse reactions observed during treatment will be closely monitored by the Clinical Trials Monitoring Committee (CTMC) on a monthly basis. The CTMC is responsible for data and safety monitoring of the trial and adherence to the DSMP, and is serving as the Central DSMB for this study. The independent Quality Assurance Committee (QAC) is responsible for oversight of the operation of CTMC, including adherence to the DSMP. Reports from the CTMC are reviewed monthly by the QAC.

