#### C. Molecular characteristics.

The following variables are known to influence efficacy of tamoxifen in the treatment of BC patients and will be analyzed at a later date.

*Endoxifen levels* – continuous, time-varying. These data will be available at t1 and t2.

*CYP variants* - dichotomous (yes/no), constant over the study period.

In addition to testing their significance as effect modifiers, we will also examine their relationship with the outcome variables (MBD, cytomorphology, proliferative index, etc) to validate known relationships. Proc Mixed for normal data and Proc GLMMIX for non-normal data in SAS 9.1 (Cary, North Carolina) will be used for analysis.

***Exploratory Aim 2: To examine the relationship between a low-dose tamoxifen regimen and clinical measures of efficacy and toxicity.***

For measures of clinical efficacy, we will document the occurrence of new breast cancer and DCIS diagnoses.

The assessment of clinical toxicity will include the following outcomes/measures:

- 1) incidence of uterine and other cancers during the study;
- 2) gynecological symptoms: any and the frequency of hot flashes, night sweats, vaginal discharge, vaginal bleeding or spotting, missed menstrual periods for pre-menopausal women, genital itching/irritation, and pain with intercourse, to be obtained from symptom log administered 10 times (baseline, days 28, 90, 180, 270, 365, 455, 540, 630, 730) ;
- 3) incident thromboembolic events (DVT, PE, TIA or stroke, and retinal vein thromboses);

4) incidence of cataract;

5) liver function abnormalities: total bilirubin, SGOT/AST, SGPT/ALT, measured at baseline, year 1, and year 2.

The *incidence* of new breast cancer, DCIS, non-breast malignancies, thromboembolic events, and cataract are expected to be low ( $\leq 5$  events per arm) during the study period given the sample size, based on statistics quoted in Investigational Brochure. Thus, we will initially compare the frequency of events by treatment group in a 2x2 table using the Fisher exact test, stratified on CYP2D6 status. We will also use poisson regression in cohort analysis to examine treatment differences in these outcomes adjusted for covariates, including CYP2D6.

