
***Exploratory Aim 2: To examine the relationship between a low-dose tamoxifen regimen and clinical measures of efficacy and toxicity.***

This aim will also be considered exploratory as the study was not powered to detect treatment difference in these adverse outcomes. As the events of interest have very low incidence rates in both treatment groups (see Table 3 of Investigational Brochure), the study will not have any power (<5%) to detect the relative risks seen in NSABP P-1 Trial. The power for detecting treatment differences in the proportion of women anticipated to experience hot flashes and gynecological symptoms is somewhat better, 90% for vaginal discharge (prevalence rates of 35% in placebo and 55% in treatment groups), but only

41% for hot flashes (prevalence rates of 68% in placebo and 80% in treated groups), and 5% for vaginal bleeding (22% versus 23%).

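### The efficacy stop at a breast cancer risk ratio of 0.14 has no minimum event count and no look schedule, so one placebo case against none would halt the trial

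*Combined protocol and SAP*

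**What the plan says.** Section 6.4.2 sets the rule: "Thus, if a risk ratio of 0.14 or less is observed during DSMB review, the trial will be halted and subjects unblinded". The threshold is the estimate from one subgroup of the standard-dose prevention trial (NSABP P-1): "the subgroup of women with a prior history of atypical hyperplasia had a reduction in breast cancer risk of 86" percent, with a 95% CI for the ratio of 0.03 to 0.47. The same section gives 0.51 for that trial as a whole, and says that low-dose tamoxifen is not expected to do better than the standard regimen.

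No section says when the efficacy ratio is read. The only stated review frequency, in Section 8.2.3, concerns safety: "Adverse reactions observed during treatment will be closely monitored by the Clinical Trials Monitoring Committee (CTMC) on a monthly basis". That committee also serves as the central DSMB.

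Elsewhere the plan treats clinical events as exploratory. Under Exploratory Aim 2 in Section 12.4, the incidences of "new breast cancer, DCIS, non-breast malignancies, thromboembolic events, and cataract are expected to be low", at 5 events or fewer per arm. Under the same aim in Section 12.5, "the study will not have any power (<5%) to detect the relative risks seen in NSABP P-1 Trial".

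**The concern.** The wording leaves no discretion, and the quantity it acts on is unstable at the event counts the plan expects. With 1 to 7 placebo cases, the ratio is 0.14 or less only if tamoxifen has no cases. One tamoxifen case needs eight placebo cases. Under frequent review, the rule therefore mostly records which arm has the first cancer. By contrast, the thromboembolism rule in Section 6.4.1 does name a count (two grade 4 cases against none).

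A halt with unblinding on one or a few events would end the randomized, blinded comparison on no evidence of benefit. Accrual is staggered, so most such halts would come while most women are short of 24 months. The blinded, on-treatment two-year density data, on which the primary analysis rests, would then largely be lost. The harm comes from halting. The rule does not inflate the type I error of the density test.

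**Working it through.** **The plan's own figure.** The documents give no operating characteristic for this rule. The nearest figure is the under-5% power for clinical events, and it reproduces. With the P-1 breast cancer rates in Section 3.3 (6.5 v 3.6 per 1000 per year, so 1.3% v 0.72% over two years) and 115 per arm, exact Fisher power is 0.2%.

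**What one event says.** For 0 v 1, the exact 95% upper limit for the tamoxifen share of cases is 1 - 0.025 = 0.975. The upper limit for the ratio is 0.975/0.025 = 39. Fisher p-values for 0/115 v k/115 are:

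| Placebo cases k | 1 | 2 | 3 | 4 | 5 | 6 |
|---|---|---|---|---|---|---|
| p | 1.00 | 0.50 | 0.25 | 0.12 | 0.060 | 0.029 |

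All six splits meet the stopping rule. Only the last falls below 0.05.

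**Inputs for the false-stop probability.**
- 115 per arm (Section 12.5) and 24 months of treatment (Section 6.1).
- Event rate: assumed at 0.5% to 2% per year, anchored in Section 2.1. One cohort reports that "by twenty-five years of follow-up, the cumulative risk of BC was 12.2" percent, and 1 - 0.878^(1/25) = 0.52% per year. Two others report "cumulative incidence of BC to be 13.9% and 12.9% by age 40 and 20% and 22% by age 45". Conditional on reaching 40 without breast cancer, (0.20 - 0.139)/0.861 over 5 years is 1.46% per year, and (0.22 - 0.129)/0.871 over 5 years is 2.18% per year.
- Expected cases per arm: 115 x (1 - e^-0.01) = 1.1 to 115 x (1 - e^-0.04) = 4.5, within the plan's ceiling of 5.
- Accrual: the documents give no total period. Section 4.0 shows that it ran past two years: "After the initial two years of accrual, we observed an average recruitment yield of only 14" percent. I assumed uniform entry over 24 to 60 months.
- Look schedule: varied, because none is stated.

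**Closed form.** If the ratio is read almost continuously and the drug does nothing, a stop needs at least one case and the first to be on placebo. With mu expected cases per arm, the probability is about 0.5 x (1 - e^(-2 mu)). That is 44.5% at mu = 1.1, with a ceiling near 50%. For a single look at the end with mu = 1.14, (1 - e^-1.14) x e^-1.14 = 22%.

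**Simulation, no drug effect** (20,000 trials per setting; stop when placebo cases exceed 0 and tamoxifen cases are at most 0.14 times placebo cases):

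| Ratio read | False stop, accrual 24-60 months | False stop, simultaneous entry | Share of stops at exactly 1 v 0 (accrual 24-60 months) |
|---|---|---|---|
| Monthly | 44-49% | 45-47% | 96-99% |
| Half-yearly | 38-45% | 24-38% | 80-96% |
| Yearly | 30-41% | 9-32% | 69-91% |

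A single look at the end gives 1-22%. With accrual over 24 to 60 months, the share of stops with fewer than half of the 230 women at 24 months is 88-100% read monthly and 77-99% read yearly.

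A second simulation used blocks of 4, 1 to 5 expected cases per arm and accrual over 2 to 7 years. It gave 42-50% monthly and 28-44% yearly. Adding 10% yearly dropout at four-year accrual gave 46-48% and 35-40%.

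**If tamoxifen doubled the risk**, the first case would fall on placebo about one time in three. The simulation gives an efficacy stop in 31-33% of trials read monthly and 15-27% read yearly.

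**The case against.** The strongest objections concern the size of the problem.

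- **Event rate.** The rate anchors come from childhood-cancer cohorts, while eligibility extends to other primary cancers, total body irradiation and exposure up to age 40. Section 2.1 puts survivors of other cancers at only about twofold risk. Lower rates are plausible: at 0.2% per year the false-stop probability is about 30-31% monthly and 28% yearly, and at 0.35% it is 39-40% and 35-37%. The plan's ceiling of 5 is also ambiguous, since it may apply to each listed outcome or to all together.
- **Detection.** Cancers may surface mainly at the annual mammograms. If all were found then, the yearly-look range widens to about 23-41%. The share of stops before half of the women reach 24 months becomes about 70-99% read yearly and 82-100% read monthly. Monthly false-stop rates barely change.
- **Data loss.** Section 6.4.2 does not say that imaging ends at a halt. Annual mammography is standard care, and the mixed model keeps every woman with a baseline image. What is lost is the blinded, on-treatment two-year data, not every later image.
- **Judgement.** A DSMB would probably not halt on 1 v 0, and the rationale in Section 6.4.2 points to a clinically meaningful reduction. But the sentence is mandatory as written. If judgement is intended, it has to say so.

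The first three points stand as widenings of the ranges. None removes the defect, because only a single look at the end brings the false-stop probability much lower across the range of rates, and that is no longer an early stop.

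**Conclusion.** The concern holds and should be corrected. That 1 v 0 satisfies the rule is arithmetic and needs no assumption beyond counting zero cases against one as a ratio of 0. The false-stop probability of about 44-49% monthly or 30-41% yearly rests on 0.5% to 2% per year, constant risk over 24 months, accrual over 24 to 60 months, and the rule being applied whenever the ratio qualifies. At rates as low as 0.2% per year it is still about 28-31%. The monthly figure uses the only review frequency in the documents, but that frequency is stated for adverse reactions and not for efficacy.

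**What to change.** In Section 6.4.2, delete the hard stop at 0.14 and have breast cancer counts by arm reported to the DSMB descriptively.

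If an efficacy stop is kept, replace the bare ratio with a minimum total event count or an exact-test boundary, and state the look schedule and the false-stop probability. State also whether DCIS counts: Section 6.3 includes it in a breast event, and Section 6.4.2 is silent. Options, read monthly under no drug effect:
- **At least 4 total events:** false stop in about 1-6% of trials. As a check, the chance that the first four cases all fall on placebo is 0.5^4 = 6.25%. A 0 v 4 split (p = 0.12) would still halt the trial.
- **At least 6 total events:** about 0.03-1.9% (0.5^6 = 1.6%).
- **Exact p < 0.001:** needs 11 v 0, since 2 x 0.5^11 = 0.00098. With 5 or fewer events expected per arm, this is practically the same as deletion.

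The edit is one sentence. The cost is giving up an early efficacy stop on an exploratory endpoint. An event floor keeps little of it: even if the true ratio were 0.14, the 6-event version would stop only about 0.1-20% of trials.

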## 7.0 TREATMENT PLAN

### 7.1 **Subject Treatment**

Subjects will be randomized 1:1 to receive low-dose tamoxifen 5 mg or placebo daily for 24 months.

Subjects will be instructed to swallow the capsule whole, with water or another non-alcoholic liquid, preferably the same time each day. They may take the tamoxifen capsules with or without food. If they forget a dose, participants will be asked to take it when they remember, and then take the next dose as usual, but if they do not remember until their next dose, to not take extra capsules to make up the missed dose.

For premenopausal subjects, they will be instructed to begin their study medication course while menstruating or after a negative beta-HCG or serum pregnancy test as below. For premenopausal subjects who do not have regular menstrual periods or are between periods, a beta-HCG level will be performed to confirm that the patient is not pregnant before starting study medication. Participants will be warned that they should avoid pregnancy while taking study medication and for two months after discontinuation. If they are sexually active, they will be advised to use barrier or nonhormonal contraceptive measures while on study.

### 7.2 **Concomitant and Repeat Therapy**

No concomitant therapy is allowed with the exception of continued medications for chronic illnesses that are not excluded in Section 5.0, and necessary medications for unrelated acute illnesses that may occur during the study (cold, flu, infection, etc.). Any such medications must be recorded. Ingestion of certain natural products should also be monitored while on trial, as outlined in Section 11.14.

### 7.3 **Criteria for Removal from Treatment**

7.3.1 Treatment will be discontinued if a subject experiences an adverse event which the investigator deems related to the study medication or which will interfere with the ability of the subject to comply with the protocol. See section 6.3 for specific rules.

7.3.2 A subject may always voluntarily withdraw from treatment whenever she wishes.

## 8.0 TOXICITIES TO BE MONITORED AND DOSAGE MODIFICATIONS

NCI CTCAE v.4.0 will be used to assess toxicity, study and medication stopping rules are outlined in Sections 6.3 and 6.4, respectively. The study will utilize Adverse Event

Collection Form for reporting all AEs and the FDA MedWatch for reporting serious adverse events as defined below.

## 8.1 Dosage Changes Based on Toxicity

There will be no dose modifications on this trial. See Section 6.3 for discontinuation rules.

## 8.2 Data Safety and Monitoring

### 8.2.1 Monitoring and Personnel Responsible for Monitoring

This is a multi-center phase II trial conducted at the University of Alabama at Birmingham and participating institutions, and monitored by the Clinical Trials Monitoring Committee (CTMC) housed at the UAB Comprehensive Cancer Center.

### 8.2.2 Adverse Events: List and Reporting Requirements

Adverse event (AE) monitoring and reporting is a routine part of every clinical trial. Serious Adverse Events (SAEs) are reported by the site PI within 24 hours to the coordinating center ([[contact]](mailto:[contact]), [contact]). The Coordinating Center is then responsible for reporting SAEs to the UAB IRB and Clinical Trials Monitoring Committee in accordance with study-specific requirements. SAEs occurring at participating sites are reported to the UAB IRB as “non-UAB” events.

A Serious Adverse Event (SAE) is an AE that 1) results in patient hospitalization or prolongation of hospitalization; 2) results in persistent or significant disability or incapacity; 3) results in death; 4) is a cancer or congenital abnormality or 5) results in the development of drug dependence or abuse. An AE must be considered an SAE when the nature or severity of the event is not consistent with the current Investigator’s Brochure. Participating site SAEs must be reported by the site PI to the coordinating center as described above. It is also the responsibility of the site PI to report SAEs to the site IRB and to submit copies of that report to the coordinating center. It is the Coordinating Center’s responsibility to report the SAE to the appropriate regulatory agency and / or industry sponsor. This submission of IND Safety Reports will be cross referenced according to local regulations to Onyx Investigational Compound Number (IND) at the time of submission.

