### 3.5 **Supplier**

Tamoxifen is commercially available in 10 mg and 20 mg tablets. For this trial, generic 5mg capsules and matching placebo capsules will be manufactured by Sharp Clinical Services.

Tamoxifen and matching placebo will be manufactured as a capsule for oral administration. Each 5 mg tamoxifen capsule contains 7.6 mg of tamoxifen citrate, which is equivalent to 5 mg of tamoxifen, as well as anhydrous lactose, colloidal silicon dioxide, crospovidone, magnesium stearate, microcrystalline cellulose and sodium lauryl sulfate, as inert excipients. Matching placebo capsules will contain anhydrous lactose.

For this study, blistered cards will contain a month's supply of tamoxifen 5mg or matching placebo capsules.

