Serious adverse events (SAE) and all grade 3-4 toxicities with *possible* or greater attribution to the study drug must be submitted to the coordinating center PI and study staff immediately (within 24 hours of knowledge of the event), to allow reporting to the local and central IRBs and the central DSMB. If a Grade 3-4 AE is determined to have *possible* attribution to low-dose tamoxifen, an AE report will be submitted to the Food and Drug Administration (FDA) as described in Section 8.0.

Because venous thromboembolic events have been associated with standard dose tamoxifen, we include CTCAE specific to DVT, PE, and stroke below.

**CATEGORY:** VASCULAR

**Adverse Event:** Thrombosis/embolism (vascular access-related)

**MedDRA Code:** 10062169

Grade	Description
1	Venous thrombosis (e.g., superficial thrombosis)
2	Venous thrombosis (e.g., uncomplicated deep vein thrombosis), medical intervention indicated
3	Thrombosis (e.g., uncomplicated pulmonary embolism [venous], non-embolic cardiac mural [arterial] thrombus), medical intervention indicated
4	Life-threatening (e.g., pulmonary embolism, cerebrovascular event, arterial insufficiency); hemodynamic or neurologic instability; urgent intervention indicated
5	Death

The following are considered clear indications for discontinuation of study protocol therapy (confirmed by clinical diagnosis):

- Deep venous thrombosis (DVT)
- Pulmonary embolism (PE)
- Transient ischemic attack (TIA)
- Cerebral vascular accident (CVA)
- Retinal vein thrombosis
- Cardiac ischemia/infarction

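### Section 8.2.2 leaves life-threatening events out of the SAE definition, treats inconsistency with the Brochure as seriousness, and cites an Onyx IND that needs confirming

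*Combined protocol and SAP*

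**What the plan says.** Section 8.0 states that the trial will use the "FDA MedWatch for reporting serious adverse events as defined below", so the definition in Section 8.2.2 is the operative one. That definition begins: "A Serious Adverse Event (SAE) is an AE that 1) results in patient hospitalization or prolongation of hospitalization". The second and third criteria are disability or incapacity, and death. The fourth is a cancer or congenital abnormality, and the fifth is drug dependence or abuse. The list ends there.

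The next sentence adds a further entry route: "An AE must be considered an SAE when the nature or severity of the event is not consistent with the current" Investigator's Brochure. It sets no minimum grade or outcome.

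The paragraph closes by requiring that IND safety reports be "cross referenced according to local regulations to Onyx Investigational Compound Number (IND) at the time of submission". Section 3.5 describes the study drug differently: "generic 5mg capsules and matching placebo capsules will be manufactured by Sharp Clinical Services".

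Section 6.3 has a parallel rule. SAEs, and grade 3-4 toxicities of *possible* or greater attribution, go to the coordinating center within 24 hours. Its grading table for thrombosis and embolism describes grade 4 as "Life-threatening (e.g., pulmonary embolism, cerebrovascular event, arterial insufficiency); hemodynamic or neurologic instability; urgent intervention indicated".

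**The concern.** Seriousness and expectedness are different attributes. Seriousness describes what the event did or threatened to do. Expectedness describes whether its nature and severity are already known. Section 8.2.2 mixes the two and leaves out one component of seriousness.

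- **Omission.** A threat to life is not a route to SAE status, although the trial's own grading table recognises that level of severity and Section 6.4.1 builds a stopping rule on grade 4 thromboembolism.
- **Over-inclusion.** Any event that does not match the Brochure becomes an SAE, however mild. This includes a listed event of unexpected severity as well as an unlisted one.
- **Cross-reference.** Safety reports are tied to an IND under a company name for which the supplied text gives no role.

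At stake is the quality and speed of expedited safety reporting. Some events that the monitoring committee should see quickly have no fast route, and the fast route also carries minor ones.

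**Working it through.** No arithmetic decides this point, and the plan gives no figure to reproduce. The check sets the sections side by side and traces which events reach a 24-hour report. It assumes that a life-threatening event is graded 4, as in the Section 6.3 table.

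| Event | Meets one of the five criteria (8.2.2) | Caught by the Brochure sentence (8.2.2) | Caught by the grade 3-4 route (6.3) | 24-hour report as written |
|---|---|---|---|---|
| A. Life-threatening, admitted to hospital | yes | not needed | not needed | yes |
| B. Life-threatening, none of the five, inconsistent with the Brochure | no | yes | not needed | yes |
| C. Life-threatening, none of the five, consistent with the Brochure, attribution *possible* or greater | no | no | yes | yes |
| D. As C, but attribution below *possible* | no | no | no | **no** |
| E. Grade 1, inconsistent with the Brochure | no | yes | no | **yes** |

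Row D is the gap and row E is the over-reporting.

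**What happens to row D instead.** The study calendar schedules the Adverse Event Collection Form at Days 180, 365, 540 and 730. The intervals are 180, 365 − 180 = 185, 540 − 365 = 175, and 730 − 540 = 190 days. In-person visits carry a window of 60 business days either way, and Section 9.4 allows 28 days for forms. A row D event could be reported sooner, but none of the rules traced here requires it within 24 hours.

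**Is expectedness treated separately elsewhere?** Yes. Section 6.4.1 holds accrual on repeated toxicities that are related, unexpected and grade 3-4, naming each attribute in its own right. The Brochure comparison is the natural test for the second of these; Section 8.2.2 applies it to the wrong attribute.

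**Does any analysis use SAE status?** No. Section 12.4, Aim 2, tabulates grade 2-4 toxicities by arm with Fisher exact tests, and the adverse-event power statement in Section 12.5 uses the same measure. The rules in Section 6.4.1 rest on grade, attribution, expectedness and named events. The rule in Section 6.4.2 rests on a risk ratio for breast cancer.

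**Do the two corrections interact?** Yes. If the Brochure sentence were removed alone, a row B event with attribution below *possible* would lose its only 24-hour route and the gap would widen. With life-threatening added at the same time, rows B and D are both SAEs and row E is not.

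**Onyx.** The name appears once in the supplied text, in Section 8.2.2. Section 3.5 names a different manufacturer and a generic drug.

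**The case against.** The strongest reply is that the practical harm is small. Most life-threatening events will involve admission and so qualify under the first criterion. The Brochure sentence catches those that are unexpected, and Section 6.3 catches those that may be related. Site investigators must report adverse events to the coordinating center in any case, and Section 8.2.3 has the monitoring committee, acting as the DSMB, review adverse reactions monthly. Over-reporting errs on the side of caution and costs only effort. Most of this stands, and it is why the gap must be stated with all of its conditions. It does not make the definition right: row D still lacks a fast route, and monthly review can cover only what has been reported.

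Four stronger readings are tempting, and the documents do not support them.

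- A reader might infer that SAE counts by arm would be distorted and the safety comparison biased. No SAE comparison by arm is planned.
- A reader might infer that any grade 4 event judged unlikely to be related and managed without admission escapes 24-hour reporting. It does so only if it also meets none of the other four criteria and is consistent with the Brochure.
- A reader might infer that the thromboembolism stopping rule would miss events. That rule does not use SAE status, and clinically diagnosed DVT, PE, TIA and CVA each trigger discontinuation under Section 6.3. Events rated unrelated by the site, including placebo events that enter the 1.4 risk ratio, could arrive later; that concerns speed rather than capture.
- A reader might infer that Onyx is an unrelated company and that reports would go to the wrong file. Front matter was removed from the supplied text, so a role stated there cannot be ruled out.

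**Conclusion.** The point holds as two drafting errors in the operative reporting rule and one reference to verify.

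1. Life-threatening events are missing from the SAE criteria. The consequence is confined to events that meet none of the five criteria, are consistent with the Brochure, and are rated below *possible* attribution. These are not SAEs and have no 24-hour route.
2. Inconsistency with the Brochure confers seriousness at any grade, so minor events enter expedited reporting to the IRBs, the monitoring committee and regulators. The planned grade 2-4 comparison is unaffected.
3. The Onyx IND is not shown to belong to this trial. The documents support a query, not a finding that it is wrong.

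Neither the number of row D events nor the number of row E events can be estimated: the Brochure is not supplied, and the plan gives no rates for either. The conclusion assumes that Section 8.2.2 is followed as written and that no supplementary procedure redefines an SAE. The errors should be corrected because this is the rule that sites are told to follow; they do not threaten the trial's efficacy result.

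**What to change.** Amend Section 8.2.2 in one step:

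- Add life-threatening to the seriousness criteria.
- Take the Brochure sentence out of the definition of seriousness and use it only to judge expectedness, which the accrual hold in Section 6.4.1 needs.
- Confirm the IND cross-reference, or replace it with this trial's own IND or exemption.

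The first two changes must be made together, because removing the Brochure sentence alone would widen the gap. Section 6.3 should be read against the revised text so that the two 24-hour routes agree.

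The cost is a short protocol amendment and a retraining note to sites. It should reduce unnecessary 24-hour reports. It changes no dose, treatment, stopping rule or planned analysis.
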